1.3 RATIONALE FOR PERFORMING THE TRIAL

No approved treatments are available to diminish inflammation and tissue destruction in patients with bronchiectasis (BE), a chronic lung disease with neutrophilic bronchial inflammation. There is a high unmet medical need to break the vicious cycle of recurrent severe infections and further airway damage.

████████ will provide information on the efficacy, safety and optimal dosing regimen of BI 1291583 in preventing pulmonary exacerbations in patients with BE not related to CF. Approx. 240 BE patients, with a diagnosis confirmed by a CT scan, who are regular sputum producers and have had at least 2 pulmonary exacerbations in the previous year, (alternatively 1 pulmonary exacerbation plus high symptom burden as measured by the SGRQ questionnaire, [Appendix 10.4.1](#)), will be enrolled in a 2:1:1:2 ratio to receive once-daily oral doses of 5 mg, 2.5 mg, 1 mg of BI 1291583 or placebo. Commonly used stable maintenance treatment will be allowed as background treatment.

Trial 1397-0013 (ClairaflyTM) is mirroring the first 12 weeks of █████ and is by that adding important information on safety and PK similarity across bronchiectasis patients with and without CF treated with BI 1291583 5 mg qd or placebo.

Downstream suppression of NE activity will be used to link clinical outcomes assessed in █████ as established surrogate biomarker for exacerbations.

In order to be able to address future scientific questions, trial participants will be asked to voluntarily donate biospecimens for banking (please see Section [5.5](#)).

If the trial participant agrees, banked samples may be used for future biomarker research and drug development projects, e.g. to identify patients that are more likely to benefit from a treatment or experience an adverse event (AE), or to gain a mechanistic or genetic understanding of drug effects and thereby better match patients with therapies.

Agreement on this banking is not a requirement for study enrolment.

1.4 BENEFIT - RISK ASSESSMENT

1.4.1 Benefits

BI 1291583 is a potent CatC inhibitor with an expected inhibition of 99% in the bone marrow for the dose included in this study and is expected to improve the protease-antiprotease balance in the lungs of patients with chronic neutrophilic airway inflammation. The central role of neutrophilic inflammation driven by serine proteases is well described in both, CFB and NCFB. A complex interplay between infection and inflammation feeds the pro-inflammatory vicious cycle that drives the destruction of pulmonary architecture.

Inflammatory immune cells (mainly activated macrophages and neutrophils) represent the major infiltrating population in disease conditions associated with BE and contribute significantly to tissue damage and BE generation.

Cell-derived proteases and reactive oxygen species represent key mediators and particularly the protease-antiprotease imbalance is considered as key pathogenic component in degrading extracellular matrix [[R21-3308](#)].

Treatment with BI 1291583, and hence suppression of NSPs, has the potential to provide significant benefit to patients by disrupting this vicious cycle. Associated benefits would be sustained tissue protection and reduced symptoms (e.g. cough, volumes of sputum), prolonged time to exacerbation and reduction in exacerbation frequency, as well as better maintained quality of life and potentially even a reduction in mortality.

This premise has already been partially validated by the outcome of the Phase II study of the CatCi brensocatib in the NCFB WILLOW study [[R21-0168](#)].

Patients with CFB receiving the CatC inhibitor BI 1291583 in this ‘first-in-CF-patient’ trial may have a transient direct medical benefit from participation, as a treatment duration of 12 weeks is not expected to have a permanent impact on the long-term course of their disease. However, the NE pathway is anticipated to play an important role in bronchiectasis as sputum NE activity was found to be a biomarker of disease severity and future risk of exacerbations in patients with bronchiectasis [[R18-3321](#)]. For this trial, patients will be selected that have a history of pulmonary exacerbations, indicating that the targeted pathway is active. Considering the study treatment duration of 12 weeks, inhibition of NE activity may result in modulation of clinical efficacy endpoints. Some benefit in symptoms (e.g., sputum

volume, cough, mucus plugging), [REDACTED] might be expected with administration over 12 weeks.

In patients treated with placebo, no benefit is expected beyond the general benefits of regular medical assessment during participation in a clinical trial. All participants will have a close safety monitoring of their health status throughout the trial.

1.4.2 Risks

Factors of risks may derive from knowledge regarding the mode of action (MoA), the nature of the target, findings in animal models / non-clinical safety studies, and findings from clinical studies.

The clinical data of BI 1291583 showed an acceptable safety profile in healthy volunteers. A Phase II trial in patients with [REDACTED] A Phase II trial with another CatC inhibitor, brensocatib, in NCFB showed that 24 weeks treatment resulted in a slightly increased occurrence of periodontal disease and skin exfoliation in patients receiving brensocatib compared to those with placebo [R21-0168]. Despite the increase of periodontal diseases in patients treated with brensocatib, there was no difference among each treatment group in the progression of periodontal disease observed. In addition, the incidence rates of hyperkeratosis (trial-defined skin event of interest) were comparable across different treatment groups. No elevated risk of infection was reported in clinical studies with brensocatib. The PK – safety evaluation of brensocatib showed no clinically relevant relationships between brensocatib exposure and the incidence of adverse events of special interest (AESIs) [R22-2961].

Potential effects of life-long and complete CatC inhibition can be learned from Papillon-Lefèvre Syndrome (PLS), a rare genetic disease with loss of function mutations in both alleles of the CatC gene (see [Table 1.4.2: 1](#)).

Table 1.4.2: 1 Overview of trial related risks based on the mode of action (MoA), the nature of the target, findings in non-clinical safety studies and mitigation strategies

Possible or known risks of clinical relevance for this trial	Summary of data, rationale for the risk	Mitigation strategy
Possible effects of CatC inhibition are - Hyperkeratosis - Periodontitis, which might lead to alveolar bone resorption,	Based on observations in patients with the rare genetic disease Papillon-Lefèvre Syndrome (PLS), clinical signs and symptoms of life-long complete absence of CatC, are palmoplantar hyperkeratosis, severe	
- Exclusion of subjects with relevant immunodeficiency or receiving immunosuppressive medication or having an acute infection.- Regular clinical and laboratory monitoring for infection.- Exclusion of subjects having a history of hyperkeratosis on palms or soles.

Possible or known risks of clinical relevance for this trial	Summary of data, rationale for the risk	Mitigation strategy

loss of deciduous and permanent teeth
 
- Susceptibility to infections
	
periodontitis, alveolar bone resorption, loss of deciduous and permanent teeth, and an increased susceptibility to infections [R17-3100]. The immune-deficiency in PLS patients is generally mild [R17-3101]
	
 - Close skin monitoring throughout the study (Flow Chart and Section 5.2.5.2). - Exclusion of subjects with moderate or severe periodontal disease. Requirement of dental examination for all subjects during screening. Subjects with signs of mild periodontal disease will receive standard periodontal care. - Periodontal assessment at EOT and during the study at the discretion of the investigator - Discontinuation from trial treatment in case of severe periodontal AEs or deterioration (Flow Chart and Section 5.2.5.1). A complete / near complete loss of CatC function is not expected An independent Data Monitoring Committee (DMC) will periodically evaluate clinical trial safety data.

Effects on lung, liver, kidney and bone
	
In non-clinical studies, daily treatment with BI 1291583 was associated with changes indicative of phospholipidosis / lysosomal storage in several tissues and organ systems. Most prominently affected organs were lung, liver, kidneys, and bone. Bone findings are possibly indicative of altered bone remodeling.
 
Degenerative changes or changes in the clinical status of the animals were not observed at exposures targeted in clinical studies.
	
 - Exclusion of subjects with a relevant concomitant disease assessed as clinically relevant by the investigator, particularly gastrointestinal, hepatic, renal, pulmonary, cardiovascular, metabolic, immunological, or hormonal disorders. - Laboratory testing, including blood cell count, liver function, renal function, bone turnover biomarkers and urinalysis, as well as physical examination, will be used to monitor lungs, livers, bones, and kidneys. 
The safety margins are sufficiently high in man from preclinical species where there were findings (see Section 1.2).
 
An independent DMC will periodically evaluate clinical trial safety data.

Possible or known risks of clinical relevance for this trial	Summary of data, rationale for the risk	Mitigation strategy
Reproductive system	Genotoxicity for BI 1291583 and the [REDACTED] previously identified metabolites was not demonstrated in preclinical studies. The genotoxicity assessment has not yet been completed for the newly identified metabolite [REDACTED]. Data in humans are not available.	
- Women who are pregnant or breastfeeding will be excluded.- Women of child-bearing potential must be willing and able to use two medically approved methods of birth control, one barrier method plus one highly effective non-barrier method (Section 4.2.2.3).- Men able to father a child must be willing and able to use male contraception (Section 4.2.2.3).
Drug-induced liver injury (DILI)	Rare but severe event, thus under constant surveillance by sponsors and regulators. Although not specifically expected with this molecule or mechanism, monitoring for DILI is standard in drug development.	
- Timely detection, evaluation, and follow-up of laboratory alterations in selected liver laboratory parameters (Section 5.2.6.1.4).
Blood sampling	Blood sampling is a standard clinical procedure. As with all blood sampling, there is a risk of mild pain, local irritation, or bruising (a black or blue mark) at the puncture site. Furthermore, there is a small risk of light-headedness and/or fainting. In rare cases, the puncture site can also become infected, or nerves may be damaged, inducing long-lasting abnormal sensations (paresthesia), impaired sensation of touch and persistent pain.	
- Close clinical monitoring for AEs- Selection of experienced sites and site staff
Lung function measurements	Assessment of lung function is a standard clinical procedure that many of the patients will already have experienced. Risks and discomforts associated with lung function testing may include shortness of breath,	
- Close clinical monitoring for AEs- Selection of experienced sites and site staff

Possible or known risks of clinical relevance for this trial	Summary of data, rationale for the risk	Mitigation strategy
	dizziness, or headache during the breathing tests.	
Administration of 4 doses of inhaled salbutamol / albuterol (total dose approx. 400 µg), used as Auxiliary Medicinal Product (AMP) in this trial	Post-bronchodilator pulmonary function test is a standard test. Most common side effects of salbutamol / albuterol 100 µg includes: palpitation, chest pain, fast heart rate, shakiness, nervousness, headache, dizziness, sore throat, and runny nose	
 - Patients with concomitant cardiovascular disease that in the opinion of the investigator may put the patient at risk by participating in the study are excluded. - On-site use only and under direction of a healthcare provider. - Close clinical monitoring for AEs
Sputum induction	Sputum induction is a simple and non-invasive procedure used for patients who are not able to provide a sputum sample spontaneously. The patient inhales nebulised iso- or hypertonic saline solution, which could cause bronchoconstriction.	
 - Close clinical monitoring for AEs - Selection of experienced sites and site staff - Use of inhaled Salbutamol (Albuterol) is recommended before sputum induction if no Salbutamol (Albuterol) was administered within 4 hours at the visit for post-bronchodilator spirometry
Pandemic situations	Travelling to site, being at site for assessments (standard risk in the current pandemic situation).	
 - On-site visits are reduced to a minimum. - Testing and infection control will be done according local / national recommendations - For possible additional modifications in pandemic situation see Section 6

1.4.2.1 Risk related to the COVID-19 pandemic

The available evidence does not suggest an increased risk of acquiring an infection with a viral pathogen targeting the airways, including SARS-CoV-2, nor of a particularly more severe clinical presentation in case of such an infection, with suppression of Cathepsin C. There is no evidence to suggest an increased risk of bacterial superinfection in case of COVID-19.

An increased risk of severe COVID-19 is possible in patients with CFB due to their underlying condition but is not supported for CF patients by registry data and is not expected based on the mechanism of action of BI 1291583.

CatC inhibition is not expected to reduce the efficacy of a COVID-19 vaccine to induce an immune response; and vice versa, vaccination is not expected to reduce the efficacy of the CatC inhibitor.

1.4.3 Key safety data from clinical studies

The results of 6 Phase I trials show an acceptable safety profile in healthy volunteers at all doses tested, with no serious adverse events (SAEs), AE of special interest or death.

One subject treated with BI 1291583 (1 mg) discontinued treatment due to other significant AEs according to ICH E3 (PT 'thrombophlebitis' and 'increased CRP') which were assessed as non-drug-related. In the safety lab, vital signs and ECG data there were no clinically relevant findings. The most frequently reported adverse events (AEs) investigators considered drug-related are displayed in [Table 1.4.3: 1](#). All AEs considered drug-related were mild to moderate and resolved.

[figure not shown]
Table 1.4.3: 1 Summary of AEs considered drug related by investigators across healthy volunteer trials performed

Healthy volunteer trials performed	Summary of AEs considered drug related by investigators
1397-0001 , single-rising-dose 
• [REDACTED]• 54 healthy male subjects versus placebo. 40 subjects received BI 1291583, 14 subjects received placebo	Ten subjects (25.0%) receiving BI 1291583 and 2 subjects (14.3%) receiving placebo had AEs that were assessed as drug-related by the investigator. Drug-related AEs reported for more than 1 subject overall in the BI 1291583 groups were headache (4 cases of mild or moderate intensity) and dry skin (3 cases of mild intensity).
1397-0008 , food-effect cross-over trial 
• [REDACTED] of BI 1291583 once in the fasted state and once following a standard high-fat, high-calorie meal• 12 healthy male subjects	No investigator-defined drug-related AEs were reported.
1397-0010 , drug-drug interaction trial (itraconazole) 
• Single dose of [REDACTED] alone, followed by [REDACTED] together with multiple doses itraconazole• 14 healthy male subjects	Investigator-defined drug-related AEs were reported in 4 subjects (28.6%). The drug-related AEs were diarrhea, dyspepsia, increased alanine aminotransferase, increased aspartate aminotransferase, decreased appetite, and thermohyperesthesia. Each AE was reported in 1 subject (7.1%) only after BI 1291583 + itraconazole.
1397-0002 and 1397-0011 , multiple-rising-dose. 4 weeks treatment 
• [REDACTED]• 48 healthy male and female subjects. 36 subjects received BI 1291583, 12 subjects received placebo	Six subjects (16.7%) receiving BI 1291583 and 3 subjects (25.0%) receiving placebo were reported with AEs that were assessed as drug-related by the investigators. The only drug-related event reported for more than 1 subject overall in the BI 1291583 groups was skin exfoliation (3 subjects, 8.3%), whereas in placebo it was reported in 1 subject (8.3%). Drug-related skin events were not reported more frequently for subjects treated with BI 1291583 than for subjects receiving placebo (13.9% vs. 16.7%, respectively).

Healthy volunteer trials performed	Summary of AEs considered drug related by investigators

1397-0003, Japanese single rising dose and multiple dose study
 
• [REDACTED] single dose; 24 healthy male subjects. 18 subjects received BI 1291583, 6 subjects received placebo• [REDACTED] once daily for 4 weeks; 12 healthy male subjects.• 9 subjects received BI 1291583, 3 subjects received placebo	
Single-dose and multiple-doses in healthy Japanese subjects were well tolerated.
 
No AEs leading to treatment discontinuation, or AEs defined by the investigator to be related to the study drug were reported.

For clinical assessment of bone turnover biomarkers, following the International Osteoporosis Foundation (IOF) and International Federation of Clinical Chemistry (IFCC) recommendations [[R21-0018](#)], CTX-I and P1NP were chosen as most sensitive reference markers for bone resorption and formation, respectively.

No effects on bone turnover biomarkers were seen in the 4-week MRD studies in humans at exposures up to twofold higher than will be tested in the Phase II trials, suggesting that repeat-dose administration of BI 1291583 is not associated with any clinically relevant changes in bone turnover.

For a more detailed description of the BI 1291583 profile, please refer to the current IB for BI 1291583 [[c18711868](#)].

1.4.4 Discussion

The clinical data of BI 1291583 showed an acceptable safety profile in healthy volunteers at all doses tested, with no serious adverse events (SAEs) or adverse events of special interest (AESIs). No clinical data of BI 1291583 in patients are available to date.

In a study investigating 24 weeks of treatment in patients with bronchiectasis with the CatC inhibitor brensocatib a significant prolongation in the time to first pulmonary exacerbation was reported, even in the 1/3 colonised with *P. aeruginosa*, suggesting that pharmacological inhibition of CatC may decrease the rate of bacterial airway infections in this population

[R21-0168]. The safety evaluation of brensocatib showed no clinically relevant relationships between brensocatib and AESIs or infections [R22-2961].

Twenty-four weeks treatment resulted in a slightly increased occurrence of periodontal disease but not progression, and skin exfoliation in patients receiving brensocatib compared to those with placebo, with no relationship to dose [R21-0168]. The mechanism of action of brensocatib is the same as for BI 1291583.

Based on the properties and the mode of action of BI 1291583, no specific safety concerns for patient with CF are expected:

- No specific liability to the GI tract was identified in preclinical and clinical studies. Based on the observation of no dependency of exposures on food (fasted versus high-calory/high-fat meal), it is not expected that absorption will be affected by gastric pH or pancreatic exocrine insufficiency and the management thereof by using enzyme-replacement therapy.
- For CF patients an increased risk for periodontitis is not described.
- The pathophysiology of CF specific aquagenic palmoplantar keratoderma is different to the skin lesion related to CatC inhibition and can be clinically distinguished from hyperkeratosis.
- A treatment duration of 4 weeks (Phase I MRD trials, 9 healthy volunteers in each dose group), 12 weeks (Clairafly™, 18 patients with CF treated with BI 1291583, 5 mg) and at least 24 weeks (███████████, 80, 40 and 40 patients in respective dose groups) will provide relevant insights on the effect of BI 1291583 on bone biomarkers.
- No specific risk for extrapulmonary infections is expected in CF patients. The migration of neutrophils to the site of infection is not affected by BI 1291583. Neutrophils that lack NSPs are still equipped with other microbicidal tools, such as myeloperoxidase and the α -defensin group of antimicrobial peptides.
- No safety concerns are attributed specifically to concomitant use of modulators and BI 1291583. BI 1291583 and its metabolites are not expected to affect pharmacokinetics of CFTR modulators. BI 1291583 and its metabolites are not inhibitors of Cyp3A4 and inhibition of P-gp may only occur at higher doses (≥ 9 mg) than are used in Clairafly™. BI 1291583 and its metabolites are not critically affected by concomitant use of CFTR modulators (except lumacaftor, see Section 4.2.2). Conservatively assessed, co-administration of a CFTR modulator containing Ivacaftor may lead to an increase in exposure to BI 1291583 of max. 30%. Based on pre-clinical and clinical data to date, it is not expected that BI 1291583 will increase the risk of liver diseases as references the risk from modulator therapies.

A comprehensive safety analyses will also be performed based on all available data prior to Phase III, including ██████████, a Phase II study currently underway in patients with nCFB ██████████ 240 patients planned to be randomized (2:1:1:2) to BI 1291583 5 mg, 2.5 mg, 1 mg or placebo respectively).

To mitigate the potential risk associated with a placebo-controlled trial in this patient population, usual SoC will be allowed as stable background treatment.

To ensure safety of trial participants, an independent DMC which includes experts also in the field of CF will conduct regular reviews of all unblinded safety data.

[figure not shown]
The nature of the target and the mechanism of action of BI 1291583 are well understood. In the context of the unmet medical need and anticipated benefit of BI 1291583, the benefit risk evaluation of the compound, based upon the available preclinical and clinical information, is considered favourable.

2. TRIAL OBJECTIVES AND ENDPOINTS

2.1 MAIN OBJECTIVES, PRIMARY AND SECONDARY ENDPOINTS

2.1.1 Main objectives

The aim of the trial is to investigate whether 5 mg qd of BI 1291583 (the expected human therapeutic dose) in patients with CF is safe and to assess PD and PK. Based on these data, an across-trial comparison will be performed.

The primary objective, is to estimate the number and percentage of patients who have at least one treatment-emergent AE (TEAE) during the trial.

The secondary objective is to estimate the PD effect, at Week 8, after the first drug administration. The other secondary objective is to estimate the PK effect, after the first dose and at steady state, after multiple dosing of BI 1291583 5 mg qd.

All treatment effect estimations will be as randomised, including the effects of any changes of treatment.

2.1.2 Primary endpoint

The primary endpoint is to evaluate the occurrence of TEAEs, up to 16 weeks, from first drug administration.

2.1.3 Secondary endpoint(s)

The following secondary endpoints will be determined:

- Relative change from baseline in NE activity, in sputum, at Week 8 after first drug administration (8 weeks was chosen as timepoint for this secondary endpoint to synchronise with potential cycling antibiotic use)
- AUC, over a dosing interval (AUC_{τ}), for the first dose
- Maximum concentration (C_{max}) for the first dose
- AUC_{τ} at steady state ($AUC_{\tau,ss}$)
- C_{max} at steady state ($C_{max,ss}$)

3. DESCRIPTION OF DESIGN AND TRIAL POPULATION

3.1 OVERALL TRIAL DESIGN

[figure not shown]
This is a multi-centre, randomised, placebo-controlled, double-blind, parallel group, Phase IIa clinical trial to investigate the safety, tolerability, PD and PK of 5 mg BI 1291583 (oral, qd) in patients with CFB.

Approximately 24 eligible patients will be randomised in a 2:1 ratio to either BI 1291583 or placebo. Approximately 50% of patients will be treated with CFTR-MTs, for restricted CFTR-MT also refer to [Section 4.2.2](#). The randomisation will be stratified based on whether the patient is on stable maintenance use of CFTR-MT or not (yes / no). The stratification should assure that sufficient patients are recruited within each treatment population.

Screening of patients into any single stratum will be closed in order to ensure that not more than 18 patients are randomised into that stratum. The rationale is to assess whether both treatment populations will fit into the NCFB population regardless of their background medication.

The design outline is depicted in Table 3.1: 1.

Table 3.1: 1 Design outline

R = Randomisation

The screening period may last up to maximal 6 weeks, the planned treatment period is 12 weeks, afterwards patients are followed up for additional 28 days (REP). SoC is allowed; however for an antibiotic cycling regimen, start days of a new cycle needs to be aligned with visit schedules. The visit schedule is shown in [Figure 3.1: 1](#).

An overview of all relevant trial activities is provided in the [Flow Chart](#). For visit schedules and details of trial procedures at selected visits, refer to Sections [6.1](#) and [6.2](#), respectively.

Due to the fact that participating sites are experienced CF sites and considering a treatment duration of 12 weeks, patient loss to follow-up is assessed as minor risk. Patients who discontinue the trial early for whatever reason should perform EOT and EOS visit (refer to [Section 6.2.3](#) and [Flow Chart](#)) and will not be replaced.

An independent Data Monitoring Committee will evaluate safety and efficacy data on a continuous basis. For details please refer to [Section 8.7](#).

[figure not shown]

Figure 3.1: 1 Visit schedule

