7.1 NULL AND ALTERNATIVE HYPOTHESES

The study is exploratory in nature and no confirmatory testing will be performed. Hence no null and alternative hypotheses are defined. Any confidence intervals or p-values provided are to be interpreted in the perspective of the exploratory character of the study. A justification of the sample size is provided in [Section 7.5](#).

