7.5 DETERMINATION OF SAMPLE SIZE

For this exploratory trial, it is planned to include a total of 24 treated patients. Sixteen (16) patients will receive BI 1291583, 5 mg qd, and 8 patients will receive placebo. The planned sample size is not based on a power calculation but is considered sufficient, for the exploratory evaluation of safety, tolerability of BI 1291583, as well as to investigate PD and PK properties.

Apart from the safety assessment, NE inhibition, in sputum, is one of the main interests of the study to support further drug development decisions for BI 1291583. A variety of different effect sizes for % NE reduction were investigated, and [Table 7.5: 1](#) shows the simulated operating characteristics of the design for different scenarios and sample sizes for the active arm.

With 16 (24) patients in the active group, there is approximately 65% (70%) probability to observe a % reduction in NE activity, in sputum, of at least 80% when the true effect size is 90%. In contrast, if the true effect size is 40%, the probability to observe a % NE reduction of at least 80% would be 21%, for 16 patients in the active group, and 18% if there are 24 patients randomised, in the active group. If only 12 patients are evaluable for the assessment of % NE reduction at week 8 (e.g., due to dropouts) the increased uncertainty for a correct decision is considered acceptable.

Overall, a sample size of 16 patients, in the active group, is regarded as sufficient for the objectives of this trial.

Table 7.5: 1 Simulated probabilities for observing at least a given % reduction in NE activity, in sputum, at 8 weeks

Sample size	%Reduction	Probability to observe at least a 70% reduction (%)	Probability to observe at least an 80% reduction (%)	Probability to observe at least a 90% reduction (%)
12	95%	82.4%	75.5%	61.2%
	90%	70.0%	61.5%	45.4%
	80%	55.5%	45.7%	30.9%
	70%	45.7%	37.7%	22.6%
	50%	34.3%	25.9%	14.9%
	40%	30.1%	23.2%	12.4%
16	95%	86.9%	80.1%	64.2%
	90%	74.3%	64.7%	46.6%
	80%	57.7%	47.2%	29.5%
	70%	47.5%	36.7%	21.4%
	50%	34.4%	24.0%	12.8%
	40%	29.5%	21.1%	10.2%
24	95%	92.0%	86.0%	80.3%
	90%	80.3%	70.3%	48.4%
	80%	60.5%	47.9%	26.6%
	70%	47.8%	35.3%	17.3%
	50%	32.1%	21.2%	8.5%
	40%	26.8%	18.0%	6.9%

Assumptions: SD= 2.15 (on a log10 scale).

Simulations were performed using R Version 4.0.2, with 10000 simulation runs per scenario.

8. INFORMED CONSENT, TRIAL RECORDS, DATA PROTECTION, PUBLICATION POLICY, AND ADMINISTRATIVE STRUCTURE

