### **Change from baseline analyses**

Change from baseline in log10-transformed NE activity in sputum up to Week 12 after first drug administration will be analysed by descriptive statistics and graphical representations across all visits. Descriptive statistics of change from baseline will be presented by timepoint and treatment group.

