#### 7.5.2.2 Pharmacokinetic endpoints

[figure not shown]
The analyses of PK parameters  $AUC_{\tau}$ ,  $C_{max}$ ,  $AUC_{\tau,ss}$  and  $C_{max,ss}$  are performed according to (9.8) based on the PKS.  $AUC_{\tau}$  and  $C_{max}$  for the first dose as well as at steady state ( $AUC_{\tau,ss}$  and  $C_{max,ss}$ ) will be summarized for the active treatment group.

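### Enrolment is stratified and capped to see whether patients on and off CFTR modulators each fit the NCFB population, but no readable NE or PK summary is split by that stratum

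*Protocol*

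**What the plan says.** **Design.** Protocol 3.1: "Approximately 24 eligible patients will be randomised in a 2:1 ratio to either BI 1291583 or placebo". The stratification factor is stable CFTR-MT use, about half of the patients are expected to be on it, and neither stratum may exceed 18 randomised patients. The purpose given is to "assess whether both treatment populations will fit into the NCFB population regardless of their background medication". Protocol 2.1.1 announces an across-trial comparison, and Protocol 3.2 says the CF and non-CF data will be reviewed before future trials mix the two populations.

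**NE.** SAP 7.5.2.1: "Descriptive statistics of change from baseline will be presented by timepoint and treatment group". The % inhibition summaries are laid out in the same way.

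**PK.** SAP 7.5.2.2 says that the first-dose and steady-state parameters "will be summarized for the active treatment group". Protocol 7.2.4.2 describes PK statistics over all patients in the PK set.

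**Where CFTR-MT appears in the readable SAP.** It is a baseline characteristic taken from concomitant therapy data (7.1.2). Starting or changing it is an intercurrent event counted by arm (6.3).

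**Expected PK influence.** Protocol 1.4.4 says that exposure is not critically affected by modulators other than lumacaftor. It then adds, as a conservative assessment, that an ivacaftor-containing modulator "may lead to an increase in exposure to BI 1291583 of max. 30" per cent.

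**The concern.** The question in Protocol 3.1 concerns both CFTR-MT populations, so answering it needs NE and PK results for each. An analyst who followed only the readable text would produce one NE result per arm and one PK result for the active arm. Neither shows whether one stratum fits the NCFB data and the other does not.

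The pooled figures also depend on the CFTR-MT mix that happens to be enrolled. If that mix affects exposure or NE response, it carries through unseen into the comparison with NCFB patients, which is meant to inform later trials.

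**Working it through.** **Inputs**
- Arm sizes (Protocol 7.5): "Sixteen (16) patients will receive BI 1291583, 5 mg qd, and 8 patients will receive placebo".
- Expected split of about 12/12 (Protocol 3.1): 8 active and 4 placebo per stratum at 2:1.
- Split at the cap, 18/6: 12 active and 6 placebo in one stratum, 4 active and 2 placebo in the other.
- SD 2.15 on the log10 scale (Protocol Table 7.5: 1).
- Maximum exposure rise of 30% with ivacaftor-containing modulators (Protocol 1.4.4).
- Between-patient CV of exposure: not given. Assumed 20% to 60%.

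**1. Reproduce the plan's own figure.** Table 7.5: 1 gives 64.7% as the chance that 16 active patients show at least an 80% NE reduction when the truth is 90%. I drew each patient's log10 ratio to baseline from N(log10(1 − true reduction), 2.15) and took the median of the individual % reductions, with 100,000 runs per scenario. This gives 65.0%. At n = 12 and n = 24 it gives 61.5% and 69.8%, against 61.5% and 70.3% stated. Of the 54 cells, 53 agree within 2 points. The exception (n = 24, true 95%, at least 90%: stated 80.3%, recomputed 69.7%) does not bear on this point. The stated operating characteristics therefore describe the whole active arm.

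**2. What pooling hides for NE.** Suppose 8 active patients have a true 95% reduction and 8 have 40%. The geometric mean remaining activity is √(0.05 × 0.60) = 0.173, an 82.7% reduction. The probability that the pooled median reduction reaches 70/80/90% is:
- mixed 95%/40%: 61.0/50.5/32.9%
- uniform 82.7% in all 16: 61.3/50.6/32.9%

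The pooled median cannot tell the two situations apart.

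**3. What the mix can do to PK, as an upper bound.** If every CFTR-MT user has 30% higher exposure and a fraction p of active patients use CFTR-MT, the pooled geometric mean is multiplied by 1.3^p:
- p = 0.25: 1.3^0.25 = 1.07 (7%)
- p = 0.50, the planned mix: 1.3^0.50 = 1.14 (14%)
- p = 0.75: 1.3^0.75 = 1.22 (22%)

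The 25% and 75% mixes are the extremes under the cap (6/24 and 18/24).

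**4. What by-stratum output could show.** The 95% CI half-width for mean log10 NE change is t(0.975, n−1) × 2.15/√n. The last column is simulated as in step 1, with 200,000 runs for the stratum sizes.

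| Active n | Half-width (log10) | Fold | P(observe ≥80%) if truth 90% / 40% |
|---|---|---|---|
| 16 (pooled) | 1.15 | 14 | 65.0% / 20.8% |
| 12 | 1.37 | 23 | 61.5% / 22.7% |
| 8 | 1.80 | 63 | 56.4% / 24.1% |
| 4 | 3.42 | about 2,600 | 46.8% / 24.1% |

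On versus off CFTR-MT among active patients, separating a true 90% from a true 40% reduction means a difference of log10(0.60/0.10) = 0.778:
- 8 v 8: SE = 2.15 × √(1/8 + 1/8) = 1.07. Power at two-sided 5% is Φ(0.778/1.07 − 1.96), about 11%.
- 12 v 4: SE = 2.15 × √(1/12 + 1/4) = 1.24. Power is about 9%.

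For an observed on/off exposure ratio of 1.3, with log SD √ln(1 + CV²), the 90% CI is:
- 8 v 8: 1.09 to 1.55 (CV 20%), widening to 0.80 to 2.12 (CV 60%)
- 12 v 4: 1.06 to 1.59, widening to 0.74 to 2.28

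**The case against.** **The answer may sit in text we cannot see.** SAP 4.1, 6.5 and 7.6 and Protocol 7.2.5 are absent from the public text. The head of Protocol Section 7 refers to a separate analysis plan just after a redacted sentence. SAP 5.2.2.2 defers to a Population PK Analysis Plan. The SAP abbreviation list includes MMRM, ANCOVA and REML, which the readable text never uses. A reader might infer that no stratum analysis is planned, but the documents do not support that. What stands is narrower: no readable section commits to one.

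**Population PK is the natural place for a CFTR-MT covariate.** That is fair. But Protocol 3.2 says only that the sampling may allow covariate effects to be identified, and it speaks of differences between study populations, not CFTR-MT strata. SAP 7.5.2.2 cites a noncompartmental manual for the same parameters. A population PK model would also give no NE result by stratum.

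**The 30% is not a forecast.** A reader might infer that the protocol expects higher exposure on modulators. It does not. The figure is a conservative maximum for ivacaftor-containing products, so the 7% to 22% range is a bound. Protocol 4.1.2 also reports a plateau in CatC inhibition at 5 mg, so no pharmacodynamic consequence of such a shift is shown.

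**The trial does not set out to compare modulator users with non-users.** Correct. Protocol 3.1 asks whether each group fits the NCFB population. That still needs results by group.

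**The cells are too small.** True for inference, as the working shows. Protocol 7.1 says: "The study is exploratory in nature and no confirmatory testing will be performed". That limits by-stratum output to description. It is not a reason to leave it out, since the sponsor chose these strata knowing the total would be about 24.

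**Conclusion.** The point holds for the readable text. Protocol 3.1 sets a question about two populations, and the visible NE and PK summaries are pooled over them.

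- **PK:** at most about 14% on pooled geometric-mean AUC at the planned mix, and 7% to 22% over the mixes the cap allows. This assumes the maximum 30% rise in every CFTR-MT user.
- **NE:** the documents give no expected difference between strata, so no size can be stated. The 95%/40% example only illustrates that pooling could conceal a large one.

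It does not follow that by-stratum tables would settle the question. With 4 to 12 active patients per stratum, and an NE SD of 2.15 taken as applying to log10 change, they cannot establish similarity. The primary safety endpoint is not affected.

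**What to change.** - In SAP 7.5.2.1, add descriptive summaries or individual-patient plots by IRT CFTR-MT stratum: baseline log10 NE, and Week 8 change in log10 NE by arm.
- In SAP 7.5.2.2, add the same for AUCτ,ss and Cmax,ss in the active arm.
- Name CFTR-MT as a covariate in the Population PK Analysis Plan and carry it into the across-trial comparison.
- State that the IRT stratum defines these groups, because SAP 7.1.2 takes CFTR-MT from concomitant therapy data and the two may differ.
- State that, with about 8 active patients per stratum (4 to 12 at the cap), the results are descriptive and cannot establish similarity. No test is needed.
- If these analyses already exist in text not shown here, a sentence in the SAP saying where is enough.

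The cost is a few tables or plots and one covariate, all from data already collected. Sample size and conduct do not change.
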